6.1.1 Serum Total Testosterone

Venous blood samples will be collected for analysis of serum total testosterone by direct venous puncture at Baseline and Week 4.

Due to the possibility of diurnal variation of serum testosterone levels, blood samples to assess testosterone level should be drawn in the morning between 9:00 and 11:00hrs. Blood samples will be collected into an SST or PST tube and transferred to the lab at ambient temperature.

6.1.2 Prostate Specific Antigen (PSA),

Venous blood samples will be collected for analysis of PSA at all study visits. Blood samples will be collected into an SST or PST tube and transferred to the lab at ambient temperature.

6.1.3 Plasma Triptorelin,

Blood samples will be collected for analysis of plasma triptorelin levels at all study visits from screen onwards.

Blood samples will be collected into 5 ml Vacutainer tubes (containing EDTA and aprotinin), and will be centrifuged at 4°C at 2000 g for 15 minutes. The plasma will be rapidly transferred to two polystyrene tubes. The tubes will be stoppered (airtight) and stored at -20°C. Samples will be transferred in batches to Ipsen Pharma S.A and will be analysed by Ipsen Pharma S.A.

The analytical method that will be used to determine triptorelin in plasma samples is based on a radioimmunoassay (RIA) procedure, previously validated in the experimental conditions used at Ipsen Pharma $S.A^{(8)}$. The limit of quantification of the assay is 0.010 ng/ml.

6.2 Safety Evaluations

6.2.1 Injection Tolerability

Following each injection patients will be asked about any injection site reactions. Patients will provide feedback 24 hours post-injection which will be recorded in the patients CRF.

The following parameters will be assessed:

- Pain (severity, time of onset in relation to the injection, duration).
- Redness (severity, time of onset in relation to the injection, duration).
- Swelling (severity, time of onset in relation to the injection, duration).

Severity of injection site reactions will be graded using a 4 point scale (none, mild, moderate and severe).

6.2.2 Adverse events.

All adverse events will be reported in accordance with the UHB adverse event policy.

An adverse event is any untoward medical occurrence in a subject to whom a medicinal product has been administered including occurrences which are not necessarily related to that product.

An Adverse Event can therefore be any unfavourable and unintended sign (including abnormal lab results), symptom (such as nausea, fatigue) or disease temporally associated with the use of the medicinal product whether or not considered to be related to the medicinal product.

Pre-existing conditions that worsen during a study are to be reported as adverse events.

When the deterioration in the condition for which the study drug is being used (i.e., disease progression) is interpreted as a natural outcome of the disease, it should not be recorded as an Adverse Event.

This definition includes events occurring from the time of patient giving informed consent until the end of the study.

The safety of Decapeptyl SR by the SC route in the treatment of patients with prostate cancer will be evaluated by examining the occurrence of all adverse events, abnormal laboratory findings, the use of concomitant medications and physical examination findings

6.3 Categorisation of Adverse Events

6.3.1 Intensity Classification

Adverse events will be classified as mild, moderate or severe according to the following criteria:

- Mild: an event that is easily tolerated by the patient causing minimal discomfort and not interfering with everyday activities.
- Moderate: an event that is sufficiently discomforting to interfere with normal everyday activities.
- Severe: An event that prevents normal everyday activities.

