• Informed consent.
• Demographic details (date of birth, sex, ethnic origin, height, weight).
• Relevant medical history.
• Physical examination findings (including digital rectal examination (DRE) if this has not been done within 4 weeks prior to this visit).
• Vital signs (height, weight, sitting blood pressure, pulse rate).
• Blood samples (for analysis of serum total testosterone (STT), PSA, haematology and biochemistry).
• Urine sample (for dipstick urinalysis).
• Prior and concomitant medications.
Patient's eligibility of the study will be checked by reviewing the inclusion and exclusion criteria. Eligible patients will then return to the clinic within the following month for the Baseline visit.
At the Baseline visit:
• Patients' eligibility for the study will be re-checked.
• Blood samples will be collected for analysis of STT, PSA, plasma triptorelin and Liver Function Tests (LFTs) prior to receiving their injection.
 Any adverse events or changes in concomitant medications since the Screening visit will be recorded.
Patients who are still considered to be eligible for the study after completion of all Baseline assessments will then receive a SC injection
of Decapeptyl SR 3 mg . Subcutaneous injections should be

	-
	administered into the anterior abdominal wall. Details of any immediate injection site reaction(s) will be recorded.
	To minimise risk of tumour flare, all patients will start adjuvant therapy with an anti-androgen, cyproterone acetate (CPA). Each patient will take 100 mg CPA, three times a day, for 2 weeks starting on the day of the Baseline visit.
	24 hours after the injection, the site will call the patient to check whether there have been any tolerability issues following the injection. Details will be recorded in the patients CRF.
	One month after Baseline, patients will be required to attend the clinic for a follow up visit and repeat treatment (Visit 3). At this visit the following will occur:
	• Blood samples will be collected for analysis of STT, PSA, plasma triptorelin and liver function tests (LFTs).
	• Any new or altered adverse events or concomitant medications will be recorded.
	• Patients will then receive a SC injection of Decapeptyl SR 11.25 mg . Subcutaneous injections should be administered into the anterior abdominal wall. Details of any immediate injection site reaction(s) will be recorded.

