3.4 Study Schedule

Table 2Study Schedule

a) Assessment	Visit 1 - Screening	Visit 2 - Baseline	Visit 2a (phone)	Visit 3	Visit 3a (phone)	Visit 4	Visit 5 /ETV
Month (visits calculated using calendar months)	≤ 1 mth before D0	DAY 0	V2 + 1 Day	M1 (+ 3 days)	V3 + 1 Day	M2 (+ 3 days)	M4 (+ 3 days)
Written Informed Consent	\checkmark						
Review Inc/ Exc Criteria	✓	✓					
Record Demographics	✓						
Record Medical History (inc. prostate cancer)	~						
Digital Rectal Examination	\checkmark^1						
Physical Examination	✓						✓
Vital Signs	✓	✓		 ✓ 		✓	✓
Blood Samples (serum total T, PSA) ²	✓	✓		 ✓ 		✓	✓
Blood samples (haematology & biochemistry)	√			✓ (LFTs only)			~
Blood sample for plasma triptorelin		 ✓ 		 ✓ 		✓	✓
Dipstick Urinalysis	✓						✓
Start 2wks tx with Anti-Androgen (CPA)		 ✓ 					
Decapeptyl SR injection ³		✓ (3mg)		✓ (11.25mg)			
Injection tolerability assessment		V	✓ (24hrs after injection)	V	✓ (24hrs after injection)		
Concomitant Medications	\checkmark	✓	V	✓	V	✓	✓
Adverse Events		✓	✓	✓	✓	✓	✓
End of Study Record							✓

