3.5.3 Visit 3 (month 1)

One month after the Baseline visit (+/- 3 days), patients will be required to attend the clinic for a follow up visit and their second injection. (Visit 3). At this visit the following will occur:

- Blood samples will be collected for analysis of STT, PSA, plasma triptorelin and liver function tests (LFTs).
- Any new or altered adverse events or concomitant medications will be recorded.

Patients will then receive a SC injection of Decapeptyl SR 11.25 mg. Subcutaneous injections should be administered into the anterior abdominal wall. Details of any immediate injection site reaction(s) will be recorded.

24 hours after the injection, the site will call the patient to check whether there have been any tolerability issues following the injection. Details will be recorded in the patients CRF.

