4.1.2 Exclusion Criteria

Patients who satisfy any of the following criteria must not be included in the study:

- 1. The patient has undergone bilateral orchidectomy.
- 2. The patient is either scheduled to receive, receiving or anticipated to require any chemotherapy for prostate cancer or any other cancer during the period of his participation in the study.
- 3. The patient is either scheduled to receive, or anticipated to require any surgical intervention for their prostate cancer during the period of his study participation.
- 4. The patient has any condition that in the opinion of the Investigator may preclude the administration of subcutaneous Decapeptyl SR injection.
- 5. The patient has received treatment with any LHRHa within one year prior to study entry.
- 6. The patient has a history of hypersensitivity to Decapeptyl SR or CPA and any of their excipients.
- 7. The patient has any contraindication to treatment with anti-androgens, including, but not limited to clinically significant abnormalities in liver function.

- 8. The patient has been treated with oestrogens or steroid androgens within the 12 months prior to screening, or is receiving treatment with non-steroid antiandrogens at the time of the Screening visit.
- 9. The patient, in the opinion of the Investigator, is at risk of serious complications in the event of tumour flare (e.g. vertebral metastases threatening spinal cord compression, significant obstructive uropathy) on initiation of Decapeptyl SR treatment despite concomitant treatment with anti-androgens.
- 10. The patient has any other condition that, in the opinion of the Investigator, might increase the risk to the patient or decrease the chance of obtaining satisfactory data needed to achieve the objective(s) of the study.
- 11. The patient is likely to require treatment during the study with drugs that are not permitted by the study protocol (See Appendix 2).
- 12. The patient has received any investigational drug therapy within 30 days prior to study entry, or is scheduled to receive such a drug during the study period.
- 13. The patient has a history of, or known current, problems with alcohol abuse.
- 14. The patient has any mental condition rendering him unable to understand the nature, scope and possible consequences of the study.
- 15. The patient has previously been enrolled in the study

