6. STUDY EVALUATIONS

6.1 Clinical Laboratory Tests

Clinical laboratory tests will be performed by the UHB Pathology Department, [name]. Details of the methodology and reference ranges will be kept in the Trial Site File. Laboratory test results will be recorded on the laboratory results pages of the CRF. All clinically relevant abnormal laboratory tests occurring during the study will be repeated at appropriate intervals until they return to Baseline or to a level deemed acceptable by the Investigator or until the abnormality is explained by an appropriate diagnosis. The total blood during the whole course of the study, taken for serology, biochemistry, haematology, testosterone and PSA will not exceed 75 mL per patient

Blood samples for clinical laboratory tests will be taken at the specified study visits and will consist of the following

Haematology: approx 5mL blood will be collected into a potassium Ethylenediamine Tetra-acetic Acid (EDTA) anticoagulant tube. Parameters to be assessed will include:

- Haemoglobin
- Haematocrit
- Mean cell volume (MCV)
- Mean cell haemoglobin (MCH),
- Mean cell haemoglobin concentration (MCHC)
- White blood cell (WBC) count with differential
- Platelet count.

Biochemistry: approx 5mL blood will be collected into an SST or PST tube. Parameters to be assessed will include:

- Creatinine
- Urea
- Sodium
- Potassium
- Bilirubin
- Alkaline phosphatase (ALP)
- Alanine aminotransferase (ALT)
- Total protein
- Albumin
- Globulin
- Calcium
- Lactate dehydrogenase (LDH)
- Gamma-glutamyl transferase (GGT)
- Total cholesterol
- Triglycerides

Urine analysis (fresh urine): A dipstick analysis of pH, protein, ketones, glucose, bilirubin, blood, urobilinogen and specific gravity will be performed. Further testing (e.g., microscopy and culture) will be carried out at local laboratory at the discretion of the Investigator. Should any clinically significant finding such as infection be noticed, this should be recorded as an Adverse Event and any treatment should be recorded on the CRF concomitant medications page.

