6.3.4 Laboratory Test Abnormalities

Abnormalities in laboratory test values will only be reported as adverse events if any of the following apply:

- they result in a change in study drug schedule of administration (change in dosage, delay in administration, study drug discontinuation),
- they require intervention or a diagnosis evaluation to assess the risk to the patient,
- they are considered as clinically significant

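### The adverse event intensity scale has no laboratory criterion, so on its literal wording a symptomless laboratory AE is graded mild and the maximum-intensity table would understate it

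*Protocol*

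**What the plan says.** **Intensity scale.** Protocol section 6.3.1 applies one three-level scale to adverse events, with no exception for laboratory findings. Mild means easily tolerated with little discomfort and no interference with activities. Moderate means uncomfortable enough to interfere with them. The top level is "Severe: An event that prevents normal everyday activities".

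**What counts as an AE.** Section 6.2.2 defines an AE to cover any "unfavourable and unintended sign (including abnormal lab results"). Section 6.3.4 narrows this to laboratory abnormalities that meet at least one of three conditions: they change the study drug schedule, they need intervention or diagnostic evaluation, or "they are considered as clinically significant". None of the three requires a symptom.

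**Recording.** The AE form in Appendix 4 offers mild, moderate and severe. The SAE initial and follow-up forms ask for maximum intensity on the same three levels. None of these forms has a field for an NCI grade. On numeric values, section 6.1 says: "Laboratory test results will be recorded on the laboratory results pages of the CRF".

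**Reporting.** Section 8.4.4 plans AE summary tables by maximum intensity and codes AEs by the NCI terminology v3.0. It reports laboratory data separately through summary statistics with change from baseline, flagged values, a list of clinically significant values, and low, normal and high counts.

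**The concern.** The scale and the definition of a laboratory AE do not fit together. The scale asks how the patient felt and functioned. The laboratory rule admits events that the patient may not feel at all. A marginal abnormality and one that led to a change of study drug can then receive the same grade, and the intensity table cannot tell them apart.

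The protocol itself looks for such events. All patients take cyproterone acetate 100 mg three times a day for two weeks (3 × 100 = 300 mg daily). Exclusion 7 covers contraindications to anti-androgens, including "clinically significant abnormalities in liver function". Month 1 blood sampling includes liver tests: "Blood samples will be collected for analysis of STT, PSA, plasma triptorelin and liver function tests (LFTs"). A liver abnormality without symptoms is therefore one of the signals the safety monitoring is set up to detect.

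At stake is whether one planned safety table can show a moderate or severe laboratory event when the patient has no symptoms.

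**Working it through.** The plan gives no figure to reproduce, so the check sets the sections side by side.

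**Step 1: can a laboratory AE be symptomless?** Yes. Each of the three conditions in 6.3.4 can be met on a value alone or on the action it prompts.

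**Step 2: which level does it reach?** Take, as an illustration, a liver test rise at Month 1 with no symptoms that delays the second injection. It is an AE under the first condition of 6.3.4. Against 6.3.1:

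| Level | What 6.3.1 requires | Met? |
|---|---|---|
| Mild | tolerated, little discomfort, no interference | yes |
| Moderate | discomfort that interferes with activities | no |
| Severe | activities prevented | no |

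A smaller rise, reported only because it is clinically significant, gives the same three answers. One of three levels is reachable in both cases, so the grade carries no information about degree.

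**Step 3: does the grade reach a table?** Yes. Section 8.4.4 tabulates by maximum intensity, and intensity is the term that 6.3.1 defines and the forms collect. The NCI system appears in 8.4.4 as a coding system; the text neither adopts nor rules out its grades.

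**Step 4: when are the tests taken?** Section 6.1 lists 7 haematology and 15 biochemistry parameters: 7 + 15 = 22. In the study schedule (section 3.4), the row "Blood samples (haematology & biochemistry") is marked at screening, at Visit 3 for LFTs only, and at Visit 5. The last injection is given at Visit 3. So the full set of 22 is scheduled after dosing only at Month 4, when no dose remains. This matters for the fix: a rule that reserves *severe* for an actual change in study drug could not be met at that visit.

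**Step 5: how many patients?** The protocol gives no rate of symptomless laboratory AEs. The number of scheduled tests is not a substitute, because it counts opportunities and not misgraded events. No estimate is made.

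**The case against.** **Mild is an inference.** The protocol never says how to rate a laboratory AE. The mild level is itself worded in terms of tolerance and discomfort, so one could say the scale is silent on symptomless results. A work-up or intervention might also disrupt a patient's day, and an investigator could rate higher on that ground. This stands in part. Mild is the literal reading and the only level whose wording fits, but it is not an explicit instruction. Disruption from managing an event is also not the event that 6.3.1 grades. If investigators do depart from the wording, grading becomes inconsistent between patients, which the same fix would cure.

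**The NCI grades or another document may govern.** Being coded by NCI v3.0 could be meant to include its grades; 6.2.2 refers to a hospital AE policy that is not shown; and an analysis plan may settle the matter. It stands that the role of the NCI grades is unclear. But intensity is assigned at site, from criteria and forms that the protocol fixes. This is a rule stated badly, not a detail left for later.

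**Degree is visible elsewhere.** This largely stands. The range, change from baseline, the list of clinically significant values and AEs linked to premature withdrawal are all reported, and seriousness is assessed separately. The low, normal and high counts do not show degree, so they help only partly.

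**Treatment-emergent events.** A reader might infer that a laboratory AE present before dosing that worsens silently would drop out of the safety tables, because its intensity could not increase. The documents do not support that. Section 6.2.2 requires worsening of pre-existing conditions to be reported. The third arm of the definition in 8.4.4 admits unchanged intensity where drug relationship became possible or probable. All AEs are tabulated as well as treatment-emergent ones.

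**Conclusion.** The point holds as a minor defect in safety reporting. One intensity scale covers all AEs and contains nothing by which a symptomless laboratory AE could be graded above mild, while the protocol plans to tabulate AEs by maximum intensity. For such events the table would be biased downward.

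A reader might go further and infer that serious laboratory toxicity would be hidden or that the trial's conclusions are at risk. The documents do not support this. The primary test concerns testosterone response. The stopping provision in 8.5 counts treatment failures, and the withdrawal criteria in 4.2 do not use the intensity grade. The separate laboratory outputs and seriousness reporting are untouched.

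The conclusion assumes that investigators apply 6.3.1 as worded and that the NCI grades are not otherwise brought into the intensity field. The number of patients affected is unknown and may be small.

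**What to change.** In section 6.3.1, keep the activity scale for clinical events and add:

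- Laboratory AEs are graded by the NCI v3.0 criteria already named in 8.4.4: grade 1 is mild, grade 2 moderate, grade 3 or above severe.
- A parameter that NCI v3.0 does not grade is mild if it is clinically significant only; moderate if it needs diagnostic evaluation or non-urgent intervention; and severe if it needs urgent intervention or would warrant stopping or delaying study drug, whether or not a dose remains.

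The last clause keeps *severe* reachable at Month 4. Regrade any laboratory AE already recorded from the numeric results on the CRF. A phrase in 8.4.4 saying that intensity means this grade for laboratory AEs in the treatment-emergent definition is optional.

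The cost is a short addition to 6.3.1 and a table footnote, with no new samples or visits. Investigators must look up a grade, and some laboratory AEs will be reported at a higher intensity. The table will combine two grading bases, which the footnote should state. The protocol does not reproduce the NCI criteria, so the sponsor should check the listed parameters against them before adopting the text.

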6.3.2 Causality Classification

The relationship between the drug and the occurrence of each adverse event will be assessed and categorised as below. The Investigator will use clinical judgement to determine the relationship. Alternative causes, such as natural history of the underlying disease, concomitant therapy, other risk factors etc will be considered. The Investigator will also consult en Investigator Brochure or other product information.

Not related: Temporal relationship of the onset of the event relative to the administration of the product, is not reasonable or another cause can by itself explain the occurrence of the event.

Unlikely: Temporal relationship of the onset of the event, relative to the administration of the product, is likely to have another cause which can by itself explain the occurrence of the event.

Possibly related: Temporal relationship of the onset of the event, relative to the administration of the product, is reasonable but the event could have been due to another equally likely cause.

Probably related: Temporal relationship of the onset of the event, relative to the administration of the product, is reasonable and the event is more likely explained by the product than any other cause.

Definitely related: Temporal relationship of the onset of the event, relative to the administration of the product, is reasonable and there is no other cause to explain the event or a re-challenge (if feasible) is positive.

6.3.3 Expectedness

Adverse reactions must be considered as unexpected if they add significant information on the specificity or severity of an expected adverse reaction. The expectedness of an adverse reaction shall be determined according to the reference documents as defined in the study protocol (e.g. Investigator brochure or marketing information).

Expected: Reaction previously identified and described in the summary of product characteristics (SmPC).

Unexpected: Reaction not previously described in the protocol or reference documents.

6.3.4 Laboratory Test Abnormalities

Abnormalities in laboratory test values will only be reported as adverse events if any of the following apply:

- they result in a change in study drug schedule of administration (change in dosage, delay in administration, study drug discontinuation),
- they require intervention or a diagnosis evaluation to assess the risk to the patient,
- they are considered as clinically significant

